6.3.3. Follow-Up Contact

After 48 hours post breath test administration, all subjects will receive a follow-up safety contact. The safety contact should be completed between 48 and 96 hours post breath test administration. For subjects who have been discharged, follow-up contact will be performed via telephone contact (up to 3 attempts) by a study investigator or designee. For subjects who remain inpatient at the hospital, the follow-up will be performed in person. Safety follow-up will include a chart review as well as discussion with the subject regarding their treatment course and current status.

6.4. Assessments by Visit

6.4.1. Screening Procedures

Investigators and research staff from the Emergency Department will assist in the identification of subjects through the clinical site Emergency Departments or UNM-HSC Urgent Care clinic (part of the UNM site and located next to the ED, Cohort A only). ED Research staff are trained in the identification and referral of subjects for currently active research studies. Research staff will identify subjects by asking ED staff and providers if they are currently caring for any patients that meet the protocol case description and by evaluating potentially eligible subjects

with in Firstnet (UNM) or EPIC (HFH) who present with a reason for visit that would put them at reasonable suspicion for pneumonia (e.g. possible pneumonia, difficulty breathing, COPD etc.). Research staff will not discuss informed consent with potential study subjects or retain any PHI.

Research staff will not participate in the identification of subjects or any part of this study until they have completed required CITI training and are added as team members on the study.

A waiver of HIPAA authorization may be sought for screening purposes only, so that eligible subjects are evaluated and enrolled as soon as possible after arrival so as to complete study procedures prior to antibiotic administration. The waiver may be necessary for facilitating subject enrollment without interfering with antibiotic administration times.

Subjects meeting the eligibility criteria listed in [Section 4](#) may be enrolled in the study after the nature and purpose of the protocol have been explained to them, and they have voluntarily granted written informed consent to participate. All subjects will undergo screening prior to ¹³C-urea administration. The following safety-related procedures will be performed as part of screening for all subjects:

- Medical history ([Section 6.2.2](#))
- Physical examination ([Section 6.2.3](#))
- Clinical laboratory testing ([Section 6.3.1](#))
- Vital signs ([Section 6.3.2](#))
- Urine pregnancy testing ([Section 6.3.1](#); where appropriate)
- Measurement of body weight and height and calculation of BMI ([Section 6.2.3](#))

6.4.2. Breath Test Procedures

After successful completion of the screening procedures, subjects will undergo breath test administration. The following assessments will be conducted as part of the breath test procedures for all subjects:

- Breath sample collection ([Section 6.1.1](#))
- ¹³C-urea administration ([Section 5](#))
- Vital signs (excluding temperature; [Section 6.3.2](#))
- Monitoring of AEs ([Section 7](#))

6.4.3. Follow-Up

All subjects will undergo follow-up 48 hours following breath test administration to include:

- Follow-up Safety Contact ([Section 6.3.3](#))
- Monitoring of AEs ([Section 7](#))

6.5. Appropriateness of Assessments

Study assessments are appropriate to evaluate the objectives of the study while monitoring the safety of ¹³C-urea administration. Measurement of exhaled ¹³CO₂ levels has been widely utilized in the analysis of patients receiving oral ¹³C-urea in other indications.

6.6. Clinical Stopping Rules & Safety Data Review

This study will be discontinued if it is determined that there is a significant safety risk posed towards study subjects. Potential safety risks will be evaluated on an ongoing basis during the study by the independent medical monitor. Clinical data will be presented to the independent medical monitor in cohorts of subjects as listed in the procedure ([Section 8](#)). The independent medical monitor will adjudicate AEs and determine whether enrollment may be continued for the study. Following enrollment of the 15 subjects in Cohort A, enrollment into Cohort B will not begin until the independent medical monitor performs an overall review of safety in the cohort. If the independent medical monitor determines that no safety concerns are present, and that no increased risk is apparent for subjects with advance symptomatology (Cohort B), then enrollment may proceed with the next study Cohort. The independent medical monitor will continue to review safety data in cohorts of subjects, however enrollment may continue during review. In the event an SAE is reported in a subject, enrollment should be halted until the event can be reviewed by the independent medical monitor, and determined whether enrollment should be continued.

7. ADVERSE EVENTS, SERIOUS ADVERSE EVENTS, AND SERIOUS SUSPECTED ADVERSE REACTIONS

The investigator is responsible for the detection and documentation of events meeting the criteria and definition of an AE, SAE, or Serious Suspected Adverse Reaction (SSAR) as provided in this protocol. During the study, when there is a safety evaluation, the investigator or site staff will be responsible for detecting AEs and SAEs, as detailed in this section of the protocol.

7.1. Definition of an Adverse Event

An AE is defined as any untoward medical occurrence associated with the use of a drug in humans, whether or not considered drug related.

An AE may be any unfavorable and unintended sign (including an abnormal laboratory finding), symptom, or disease temporally associated with the use of a study medication, whether or not considered causally associated with the use of the study medication. Any abnormal laboratory value deemed clinically significant by the investigator, regardless of causal relationship, must be reported as an AE.

Examples of an AE include the following:

- significant or unexpected worsening or exacerbation of the condition or indication under study
- exacerbation of a chronic or intermittent preexisting condition, including either an increase in frequency or intensity of the condition (e.g., abnormal physical examination finding)
- signs, symptoms, or clinical sequelae of a suspected interaction
- signs, symptoms, or clinical sequelae of a suspected overdose of the study medication or a concurrent medication (overdose per se should not be reported as an AE or SAE, unless nonserious or serious sequelae occur)

The following examples are not considered AEs:

- medical or surgical procedure (e.g., endoscopy, appendectomy), although the condition that leads to the procedure is an AE
- anticipated day-to-day fluctuations of preexisting disease(s) or condition(s) (including laboratory values) present or detected at the start of the study that do not worsen
- the disease or disorder being studied, or expected progression, signs, or symptoms of the disease or disorder being studied, unless they become more severe or occur with a greater frequency than expected for the subject's condition

All AEs, whether volunteered, elicited, or noted on physical examination, and regardless of causality or seriousness, will be assessed and recorded on the CRF beginning after administration of study medication through approximately 2 hours after administration. SAEs (see [Sections 7.2](#) and [7.3](#)) will be assessed and recorded after administration of study medication through the last study follow-up (as described in [Section 6.4.3](#)).

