4. STUDY POPULATION

4.1. Inclusion Criteria

Subjects must meet all of the following criteria to be considered eligible to participate in the study:

Cohort A Only:

1. be a man or woman age 18-70, inclusive
2. have suspected bacterial pneumonia on presentation to the study site based on clinical signs and symptoms
3. be expected to be treated on an outpatient basis in the opinion of the treating clinician at the time of enrollment OR a definitive decision to admit has not been made, and the subject meets ALL of the following criteria; Pulse <125 beats per minute, Systolic blood pressure \geq 100 mmHg, Respiratory rate \leq 24 breaths per minute, Temperature $>$ 35C, and Temperature $<$ 40C. Subjects who are expected to be placed in an ED observation unit are eligible if they meet all of the defined vital sign criteria

Cohort B Only:

4. be a man or woman age 18-85, inclusive,
5. have a diagnosis of suspected bacterial pneumonia on presentation to the study site based on findings of a positive chest x-ray or advanced radiology and clinical signs and symptoms
6. be planned for admission to the hospital ward/floor in the opinion of the treating clinician at the time of enrollment
7. be capable of providing a spontaneous or induced sputum for analysis

Both Cohorts A and B:

8. be capable of completing the breath test according to the clinical judgement of the investigator
9. be able to understand the study procedures, agree to participate in the study program, and voluntarily provide written informed consent

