7.2. Definition of a Serious Adverse Event

An SAE is defined as any event that meets the following criteria:

- It results in death or is life-threatening (i.e., presents an immediate risk of death from the event as it occurred). (This criterion is not intended to include an AE that, had it occurred in a more severe form, might have caused death.)
- It results in persistent or substantial disability or incapacitation. (This criterion is not intended to include experiences of relatively minor medical significance, such as uncomplicated headache, diarrhea, or sprained ankle.)
- It results in unplanned hospitalization.
- It results in prolongation of an existing hospitalization.
- It is a congenital anomaly or birth defect.
- It requires medical or surgical intervention to prevent any of the above outcomes.

Medical and scientific judgment should be exercised in determining whether an AE is serious when considering important medical events that may not be immediately life-threatening or result in death or hospitalization, but may jeopardize the subject or may require intervention to prevent any of the other outcomes listed. Examples of such medical events that may also be considered serious include, but are not limited to, intensive treatment in an emergency room or at home for allergic bronchospasm, blood dyscrasias, or convulsions that do not result in hospitalization.

Hospitalization for elective treatment of a preexisting condition that did not worsen from baseline does not meet the definition of an SAE.

Social or convenience admission to a hospital or prolongation of a hospitalization for social or convenience reasons not associated with the occurrence of an AE does not meet the definition of an SAE.

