8.4. Planned Review Process

Frequency: Greater than 100 subjects have had the test article administered to date without the occurrence of serious adverse effects (SAEs). Therefore, this protocol intends for the safety monitoring review to be performed in cohorts as follows:

- Subjects #1 through 3 = Group 1
- Subjects #4 through 6 = Group 2
- Subjects #7 through 10 = Group 3

- Subjects #11 through 15 = Group 4
- Subjects #16 through 20 = Group 5
- Subjects #21 through 25 = Group 6
- Subjects #26 through 30 = Group 7
- Subjects #31 through 35 = Group 8
- Subjects #36 through 45 = Group 9
- Subjects #46 through 55 = Group 10
- Subjects #56 through 65 = Group 11
- Subjects #66 through 75 = Group 12

Each group of subjects will be reviewed to assess whether any SAEs or other significant safety events have occurred. Safety review will be documented using the study safety review form provided in [Appendix C.1](#), to be completed by the independent medical monitor (or appropriate designee) and acknowledged by the study investigator. If an SAE has occurred, the independent medical monitor will evaluate whether the observed SAE is definitely or possibly related to test article administration, or if there is no likely relationship between the SAE and test article.

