9.2.2. Safety Endpoints

Safety endpoints will include the following:

- Incidence of all AEs
- Incidence of death, transfer to ICU, or intubation

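### A Cohort B ICU transfer judged to be expected pneumonia progression can miss both the immediate enrolment halt and the 24-hour report, although it is a safety endpoint

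*Combined protocol and SAP*

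**What the plan says.** **Immediate halt.** Section 6.6: "In the event an SAE is reported in a subject, enrollment should be halted until the event can be reviewed by the independent medical monitor". No other single event is given this effect.

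**24-hour report.** Section 7.7 starts the clock when the investigator decides that an event meets the SAE definition. It adds death from any cause, and relationship to the study drug does not matter.

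**What is not an AE.** Section 7.1 excludes "the disease or disorder being studied, or expected progression, signs, or symptoms of the disease or disorder being studied". The same sentence restores the event as an AE if it is more severe or more frequent than expected for that subject. The section also lists as AEs any worsening of the condition under study that is significant or unexpected, and the condition that leads to a procedure. Expected progression is not defined.

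**What is an SAE.** Section 7.2 lists death or a life-threatening event, disability, congenital anomaly, prolonged hospitalization, and intervention needed to prevent one of these. It also lists this: "It results in unplanned hospitalization". It names neither ICU transfer nor intubation.

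**Safety endpoint.** Section 9.2.2: "Incidence of death, transfer to ICU, or intubation".

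**Group review.** Section 8.4: "Each group of subjects will be reviewed to assess whether any SAEs or other significant safety events have occurred". For the period after Cohort B opens, Section 6.6 says: "The independent medical monitor will continue to review safety data in cohorts of subjects, however enrollment may continue during review".

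**The concern.** The product is inhaled by patients with pneumonia, so early respiratory deterioration is both the harm that safety monitoring looks for and a possible course of the disease itself. The plan counts ICU transfer and intubation as safety endpoints, but whether such an event reaches the independent medical monitor quickly depends on its being called an SAE. That in turn depends on a site judgement, whether the deterioration was expected, for which the protocol gives no criterion and on which two lines of Section 7.1 pull in different directions.

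If the judgement goes toward expected progression, the monitor may learn of the event only with the rest of the group, and further subjects can be dosed in the meantime. The SAE table and the Section 9.2.2 incidence can then also differ for reasons of site classification alone.

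**Working it through.** The documents state no rate, power or error level on this point, so there is no planned figure to reproduce. The check has two parts.

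**1. Following one event through the text.** Take a Cohort B subject, planned for the ward at enrolment (Section 4.1, criterion 6), who is moved to ICU some hours after dosing.

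| Step | Section | If judged expected | If judged significant or unexpected worsening |
|---|---|---|---|
| Is it an AE? | 7.1 | No | Yes |
| Is it an SAE? | 7.2 | Unclear: the section opens with any event, but later speaks of judging whether an AE is serious | Yes, if a listed criterion is met |
| 24-hour report? | 7.7 | Only if the investigator decides it is an SAE | Yes, if an SAE |
| Immediate halt? | 6.6 | Only if reported as an SAE | Yes, if an SAE |
| Counted as an endpoint? | 9.2.2 | Yes | Yes |

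The last row is the same in both columns; the rows above it are not. Section 7.1 also limits the recording of non-serious AEs to about 2 hours after dosing, so on that section a later ICU transfer not classed as an SAE need not appear as an AE at all. Appendix E, Section 4.9.1, gives 48 hours instead. That difference belongs in the same reconciliation.

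**2. Exposure before group review.** Section 8.4 gives these group sizes:

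- Groups 1 to 4 (Cohort A): 3 + 3 + 4 + 5 = 15
- Groups 5 to 8: 4 × 5 = 20
- Groups 9 to 12: 4 × 10 = 40
- Total: 15 + 20 + 40 = 75, which matches the planned maximum and leaves 75 − 15 = 60 for Cohort B.

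If the event is in the k-th subject of a group of size g, at most g − k further subjects are dosed before the group is complete.

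- Worst case, k = 1: 5 − 1 = 4 in groups 5 to 8, and 10 − 1 = 9 in groups 9 to 12.
- Average if every position is equally likely, (g − 1)/2: 4/2 = 2 and 9/2 = 4.5.

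Subjects dosed while the review is under way come on top of these.

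**Illustration only.** The documents give no rate for ICU transfer or intubation, so the rate p is an assumption. The chance of at least one such event among 60 subjects is 1 − (1 − p)^60:

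| p (assumed) | Chance of at least one |
|---|---|
| 1% | 45% |
| 2% | 70% |
| 5% | 95% |
| 10% | 99.8% |

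This is the chance that the question arises, not the chance that an event is classed as expected.

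**The case against.** The case on the other side is substantial, and much of it stands.

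- **Other routes to a hold exist.** A reader might infer that an SAE is the only thing that can stop enrolment. The documents do not support that. Section 6.6 has the monitor assess risk throughout, adjudicate AEs and decide whether enrolment continues, and it sets a gate: "enrollment into Cohort B will not begin until the independent medical monitor performs an overall review of safety in the cohort". Section 8.1 allows ad hoc committee meetings, Section 3.1 sends the Cohort B clinical course to the committee, and the Appendix C.1 form has a hold option that needs no SAE. But the gate has no effect once Cohort B is open, the form is completed at review, and an ad hoc meeting needs someone to have been told. An SAE remains the only single event with an immediate halt.
- **Section 7.1 points to reporting as well as away from it.** In a subject planned for the ward, a move to ICU is most naturally read as significant worsening, and so as an AE. This makes the gap narrower. It does not close it, because the exclusion stands in the same section and nothing says which line prevails.
- **Section 7.2 covers any event.** Read literally, it needs no prior AE, and its life-threatening and intervention criteria could catch an ICU transfer. But it also speaks of judging whether an AE is serious, and Section 7.7 adds death separately, which would be unnecessary if every fatal event were already an SAE. The two readings give opposite answers for the same event.
- **Intubation and death.** A reader might infer that all three endpoint events can escape. Intubation would normally meet the life-threatening or intervention criterion, and the condition leading to it is an AE under Section 7.1. Death is always reported within 24 hours. The exposure is mainly ICU transfer.
- **Cohort A.** Criterion 3 accepts subjects for whom "a definitive decision to admit has not been made", subject to vital-sign limits. A reader might infer that later admission in the same visit for the presenting pneumonia must count as an unplanned hospitalization and halt enrolment. That lets Section 7.2 prevail over Section 7.1, the reverse of what the Cohort B gap requires. It shows an ambiguity between the two sections, not a separate error.
- **A chart review takes place anyway.** The follow-up contact at 48 to 96 hours (Section 6.3.3) includes one. It will find the event, but no rule then takes it to the monitor ahead of group review.

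**Conclusion.** The point holds in a limited form. The protocol does not say whether an ICU transfer or intubation after dosing is always handled as an SAE, and it leaves expected progression undefined. A Cohort B ICU transfer judged expected and not life-threatening can therefore miss the immediate halt and the 24-hour report while still counting as a safety endpoint.

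The worst case is 4 further subjects dosed in groups 5 to 8, or 9 in groups 9 to 12, plus any dosed during the review. That rests on three assumptions: the event is in the first subject of its group, the site classes it as expected, and no ad hoc meeting is called. The judgement at issue is expectedness, not causality, since reporting under Section 7.7 does not depend on relationship to the drug.

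This is more than missing detail, because the events are the trial's own safety endpoints and an independent monitor is already in place to receive them. It should be corrected.

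**What to change.** Reconcile Sections 6.6, 7.1, 7.2, 7.7 and 9.2.2 in one amendment:

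1. State that every ICU transfer or intubation from dosing to the follow-up contact is sent to the independent medical monitor by the existing 24-hour route and entered on the Appendix C.1 form, whether or not the site regards it as expected progression. Death already follows this route under Section 7.7.
2. State that the monitor then decides under Section 6.6 whether enrolment continues. The change concerns who is told and when; it sets no new stopping criterion.
3. In the same text, say how Sections 7.1 and 7.2 together class a same-visit admission for the presenting pneumonia in a Cohort A subject whose disposition was open at enrolment, and align the AE recording period in Section 7.1 with Appendix E, Section 4.9.1.

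The cost is a few sentences and a few more expedited forms. ICU transfer and intubation are already endpoints, so item 1 needs no new outcome data. The downside is that some reports will prove to be plain disease progression.

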6.3.2. Vital Sign Measurements

Resting vital signs will include resting blood pressure, resting pulse, respiratory rate, peripheral oxygen saturation, and temperature; temperature will only be required for vital signs collected for screening. Resting tests must be obtained after resting (seated/supine) for ≥ 5 minutes.

Vital signs including blood pressure, heart rate, respiratory rate and peripheral oxygen saturation will be recorded prior to nebulization, and following completion of sample collection. Subjects will have continuous pulse oximetry monitoring during sample collection and urea nebulization, and any change in oxygen requirement will be recorded.

Actual times will be recorded in the subject CRF.

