4.9.1 Adverse Event/Serious Adverse Event Reporting

This study is a non-interventional study. The only study related procedure the patient will experience is the urea breath test. Adverse events will be collected up until 48 hours post administration of the study drug and any noted adverse events from this time period will be followed till resolution.

A patient may experience an adverse event related to the urea breath test, which is defined as but not limited to coughing, dizziness, feeling faint or fainting. If a patient were to experience an adverse event, this must be recorded in the CRF. If the adverse event is deemed to be serious, the event must be reported by the site investigator or his/her designate to the safety monitor ([name] of UNMHSC) and the study PI ([name] of UNMHSC-EM) as soon as possible. In addition, notification shall be given in writing to the FDA and the site's IRB per the IRB's internal procedures.

Serious is defined as either:

- ◆ Death,
- ◆ Life-Threatening,
- ◆ Unanticipated Hospitalization (initial or prolonged),
- ◆ Disability,
- ◆ Congenital Anomaly, or
- ◆ Requiring Intervention to Prevent Permanent Impairment or Damage.

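### Worsening of cough after the breath test is an adverse event only relative to the subject's own condition, but the plan requires no pre-dose symptom reading, so test-related cough or breathlessness may be undercounted.

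*Combined protocol and SAP*

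**What the plan says.** Section 7.1 lists what is not an AE. Signs and symptoms of the disease under study are on that list, "unless they become more severe or occur with a greater frequency than expected" given that subject's condition. The same section gives as an example of an AE "significant or unexpected worsening or exacerbation of the condition or indication under study". It does not define what is expected. AEs are recorded "beginning after administration of study medication through approximately 2 hours after administration".

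Appendix E, Section 4.9.1, describes an AE related to the breath test as "defined as but not limited to coughing, dizziness, feeling faint or fainting".

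For vital signs the plan has a before-and-after design. Under Section 6.3.2, blood pressure, heart rate, respiratory rate and oxygen saturation "will be recorded prior to nebulization, and following completion of sample collection". Oximetry is continuous during nebulization and sampling, and changes in oxygen requirement are noted.

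The first safety endpoint in Section 9.2.2 is "Incidence of all AEs". Safety and tolerability is a stated objective in Section 2. Section 5.6 confirms that every subject receives the test article, without blinding or a dummy dose.

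**The concern.** The Section 7.1 test is comparative: a pneumonia symptom becomes an AE only when it is worse or more frequent than that subject's illness would explain. Applying it needs a reading of the symptom shortly before the dose, and the plan asks for none. Cough is where this matters most, because it is both a named reaction to the test and a symptom that many patients with pneumonia can be assumed to have on arrival. Breathlessness and wheeze are in a similar position. Section 3.1 lists difficulty breathing and wheezing among the reaction symptoms to watch for, and Section 6.4.1 looks for patients whose reason for visit includes difficulty breathing or COPD.

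At stake are the AE incidence and the tolerability conclusion. There is no control group to show how much cough would have occurred anyway, and a missing pre-dose reading cannot be rebuilt later. If worsening in subjects who already cough is put down to the pneumonia, a real effect of nebulization would be under-reported and the record would not show it.

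**Working it through.** **Step 1. Is a pre-dose symptom reading required anywhere?** The places where one could stand are:

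- Medical history (Section 6.2.2) asks for tobacco use, healthcare-associated pneumonia criteria and the chest x-ray when available. It asks for no symptom list or grade.
- Physical examination (Section 6.2.4) covers the respiratory and neurological systems, without symptom grading.
- Vital signs (Section 6.3.2) are taken before and after, but they do not measure cough or dizziness.
- The schedule (Appendix A, Table 1) has no symptom row, and AE monitoring starts at nebulization.
- The mild/moderate/severe scale (Section 7.5.1) applies to events already reported as AEs.
- The safety review form (Appendix C.1) has no field for pre-dose status.

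None requires a pre-dose record of cough or breathlessness.

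**Step 2. Would a screening note serve as the baseline?** Not reliably in Cohort B. Section 3.1 places sputum collection before the breath test, and Section 6.1.1 puts it within 15 minutes of the test, by forceful cough and with nebulized saline if needed. Unless sputum from the ED workup is used, cough may be provoked on purpose shortly before dosing.

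**Step 3. How large could the undercount be?** The plan states no cough or AE rate, so there is no figure to reproduce. The inputs are:

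- N = up to 75, of whom 15 are in Cohort A (Section 3.1).
- b = share coughing before the dose. Assumed 60-90%; not in the documents.
- w = true rate of new or worsened cough after dosing, taken as equal in those with and without cough beforehand. Assumed 10%; not in the documents.

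Judged correctly against a baseline, the counted rate is w. If worsening is never recorded in subjects who already cough, it is w(1 − b).

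| b | w(1 − b) | Expected count of 75 | Expected count of 15 |
|---|---|---|---|
| 60% | 0.10 × 0.40 = 0.04 | 3.0 | 0.6 |
| 70% | 0.10 × 0.30 = 0.03 | 2.25 | 0.45 |
| 90% | 0.10 × 0.10 = 0.01 | 0.75 | 0.15 |
| Any b, judged correctly | 0.10 | 7.5 | 1.5 |

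The shortfall is w × b × N: 0.10 × 0.60 × 75 = 4.5 to 0.10 × 0.90 × 75 = 6.75 subjects overall, and 0.9 to 1.35 of 15 in Cohort A. This is the outer end. If a fraction c of worsening in subjects already coughing is recognised, the counted rate is w(1 − b) + cwb, which rises to w as c approaches 1.

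**The case against.** The strongest reply is that the plan does have a rule and partial anchors for it. Section 7.1 ties the comparison to the subject's own condition, excludes day-to-day fluctuation without worsening, and counts an increase in frequency or intensity of a chronic or intermittent pre-existing condition. Screening includes a history and a respiratory examination. Staff observe subjects for 20 minutes (Section 3.1), oximetry is continuous, the independent medical monitor adjudicates AEs (Section 6.6), and source verification covers all recorded data (Appendix E, Section 4.9). The case report form is not among the documents, and a site may note symptoms unprompted.

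Much of this stands, and it rules out several stronger readings that a reader might infer:

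- *That counting is arbitrary, so the same data could give no subjects or most subjects with a cough AE.* Reaching most subjects would mean counting unchanged pre-dose cough, which Section 7.1 excludes. What remains open is worsening in subjects who already cough.
- *That dizziness and faintness raise the same problem.* The documents give little support for treating these as symptoms that most subjects bring with them. Section 3.1 lists lightheadedness and dizziness as signs of anaphylaxis, so new onset after dosing would ordinarily be an AE.
- *That the decision to open Cohort B turns on this.* Section 8.4 directs the group reviews to SAEs and other significant safety events. A small change in mild cough is unlikely to decide that.

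The safeguards still do not supply the missing reading. Oximetry does not measure cough. A cough judged to be expected may never reach the monitor as an AE. Source verification cannot check an item that nobody was required to record.

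**Conclusion.** The point holds as a gap in AE ascertainment. The rule for disease symptoms needs a pre-dose comparison that the plan does not require, in a study without a control group. The likely direction is an undercount of test-related cough or breathlessness. For cough, it could reduce an expected 7.5 of 75 subjects to between 0.75 and 3.0. That size rests wholly on the assumed 10% and 60-90%, on equal worsening rates in subjects with and without prior cough, and on none of the worsening in prior coughers being recorded. With partial recognition the loss is smaller. The study is descriptive and tests no hypothesis (Section 9.3.2), so no inference is invalidated. What suffers is the accuracy of the AE incidence and the ability to check it. The change should be made, because it is cheap and the data cannot be recovered afterwards.

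**What to change.** At the existing pre-nebulization vital-sign time, after any sputum collection, and again at the post-sampling vital-sign time, record cough, breathlessness, wheeze, dizziness and faintness as none, mild, moderate or severe. Give each grade a short symptom-specific anchor. The Section 7.5.1 scale should not be reused unchanged: it has no level for absence, and it grades interference with everyday activities, which suits a comparison over minutes poorly.

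Tabulate pre-to-post shifts by cohort beside the AE table, and give them to the independent medical monitor with each group review. Leave the AE decision under the existing Section 7.1 rule, and add that it is made with reference to the recorded pre-dose reading. Making every one-grade rise an automatic AE would override that section's allowance for expected fluctuation.

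The post-dose reading covers only the sampling period, within 10 minutes of nebulization under Section 6.1.1. The pre-dose reading still serves as the reference for later events. Separately, the AE window needs reconciling, since Section 7.1 gives about 2 hours and Appendix E, Section 4.9.1, gives 48 hours.

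The cost is one short block on the case report form, about a minute at each of two time points. The downside is that somewhat more mild AEs may be counted.
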